Protocol Title: COVID-19-associated coagulopathy: Safety and efficacy of prophylactic anticoagulation therapy in hospitalized adults with COVID-19

Version 1.0

April 8, 2020

Investigators:

[name], Principal Investigator

[name]

[name], PhD

[name]

[name]

Table of Contents

- 1. Background and scientific rationale**
- 2. Objectives**
- 3. Study design**
- 4. Selection of subjects**
- 5. Study procedures and evaluations**
- 6. Randomization**
- 7. Assessment of Scientific Objectives**
- 8. Withdrawal or Termination**
- 9. Study Management**
- 10. Statistical analysis and considerations**

1. Background and scientific rationale

Infection with the novel coronavirus SARS-CoV-2, first identified in Wuhan, China in late 2019, has become a global pandemic affecting over 209 countries and territories. The illness caused by SARS-CoV-2 is classified as COVID-19. As of April 8, 2020, the U.S. has by far the largest number of total cases (400,549) with a mortality rate of 3.4%. Higher mortality rates of over 5% have been seen in other countries. Although many patients may have only mild upper respiratory symptoms, some COVID-19 patients become severely ill with respiratory failure with risk of progression to multiple organ failure and development of a systemic coagulopathy with features similar to disseminated intravascular coagulation (DIC).¹ The pathophysiology of COVID-19-associated coagulopathy appears to be complex and multifactorial, involving both cellular and plasmatic elements of the hemostatic system. Development of coagulopathy has been suggested to be a predictor of mortality in patients with COVID-19.² The primary treatment of DIC is focused on treating the underlying pathology; which for COVID-19 is currently limited to supportive therapy and experimental therapeutics. Treatment with low-molecular weight heparin (LMWH) in prophylactic doses was associated with better outcomes in severe cases of COVID-19 meeting ISTH criteria for DIC in a retrospective analysis.^{1,2} The International Society of Thrombosis and Hemostasis (ISTH) has published an interim guidance document recommending thromboprophylaxis with LMWH for all hospitalized patients with COVID-19.³ However, it is not known if patients with coagulopathy from COVID-19 benefit from higher levels of prophylactic anticoagulation therapy. Presently no data exist regarding the relative safety or efficacy of intermediate-dose versus low-dose prophylactic LMWH.

This prospective, randomized, open-label, single-center interventional study is designed to compare the safety and efficacy of two LMWH dosing protocols in patients admitted to the University of Iowa Hospitals with COVID-19 who meet the modified ISTH Overt DIC criteria score ≥ 3 . Patients will be randomized to low-dose LMWH (standard of care arm) or intermediate-dose LMWH (intervention arm).

2. Objectives

- 2.1** The primary objective of the study is to compare all-cause mortality of hospitalized patients with COVID-19 coagulopathy treated with low-dose versus intermediate-dose LMWH at 30 days.
- 2.2** The secondary objectives are to determine whether the use of low-dose versus intermediate-dose LMWH has an impact on major bleeding, arterial thrombosis, venous thrombosis, ICU admission, or transfusion of blood products.
- 2.3** The exploratory objectives are to determine the effects of SARS-CoV-2 infection on laboratory coagulation parameters to better understand the mechanism of COVID-19 coagulopathy.

3. Study design

3.1. Design

This is a single center, randomized, open-label study comparing low-dose enoxaparin (40 mg SC daily or 30 mg SC twice daily if BMI ≥ 40 ; standard of care arm) versus intermediate-dose enoxaparin (1 mg/kg SC daily or 0.5 mg/kg SC twice daily if BMI ≥ 40 ; intervention arm) in hospitalized patients with laboratory-confirmed SARS-CoV-2 infection.

3.2. Rationale for enoxaparin dosing

Severe infection with SARS-CoV-2 is commonly complicated with coagulopathy. Prophylactic anticoagulation therapy was associated with decreased mortality in a retrospective analysis of Chinese patients with COVID-19 associated coagulopathy.² Pharmacologic thromboprophylaxis is standard of care for patients admitted to the hospital with severe respiratory illness and is recommended by the ISTH guidance document for hospitalized patients with COVID-19.³ Patients with a BMI ≥ 40 randomized to the standard of care arm will receive low-dose prophylaxis with LMWH but will be adjusted for weight per University of Iowa institutional recommendations.⁴ The relative safety and efficacy of low-dose prophylactic LMWH versus higher doses of LMWH is unknown. Due to potential bleeding risks with full therapeutic dose anticoagulation, the intervention arm in this study will be intermediate-dose of LMWH.

4. Selection of subjects

4.1 Inclusion criteria

Subjects must meet all the inclusion criteria to participate in this study.

- Laboratory confirmed SARS-CoV-2 infection
- Age ≥ 18 years
- Requires hospital admission for further clinical management
- Modified ISTH Overt DIC score ≥ 3

4.2 Exclusion criteria

Subjects meeting any of the exclusion criteria at baseline screening will be excluded.

- Indication for full therapeutic-dose anticoagulation
- Acute venous thromboembolism (deep vein thrombosis or pulmonary embolism) within prior 3 months
- Acute cardiovascular event within prior 3 months
- Acute stroke (ischemic or hemorrhagic) within prior 3 months
- Active major bleeding
- Severe thrombocytopenia ($< 25,000/\text{mm}^3$)
- Increased risk of bleeding, as assessed by the investigator
- Acute or chronic renal insufficiency with glomerular filtration rate (GFR) $< 30 \text{ ml/min}$ calculated by the modified Cockcroft and Gault formula
- Weight $< 40 \text{ kg}$ or $> 150 \text{ kg}$
- Known allergies to ingredients contained in enoxaparin

5. Study procedures and evaluations

5.1 Screening and enrollment

Potentially eligible patients will be identified by a healthcare professional per institutional policy on privacy. The healthcare professional will assess the eligibility of the patient by performing a chart review which will include laboratory results and weight as measured on admission to the hospital. After obtaining verbal consent from the patient to be contacted for the study, a member of the research staff will approach the patient to be part of the study. The research staff will obtain informed consent from the patient/LAR before collecting any data and performing any procedures.

5.2 Trial interventions

As standard of care, hospitalized patients with confirmed COVID-19 will be monitored for coagulopathy. Daily blood tests for platelet count, prothrombin time, D-Dimer, and fibrinogen and weekly thromboelastography will be obtained, and a daily Modified ISTH Overt DIC score will be calculated (Exhibit 1). Only patients meeting all inclusion and exclusion criteria will be asked to participate in the trial. Patients will be randomized to one of two arms:

- 1) Patients randomized to the **standard of care arm** will receive low-dose enoxaparin (40 mg subcutaneously daily if BMI <40 and 30 mg subcutaneously twice daily if BMI ≥ 40).
- 2) Patients randomized to the **intervention arm** will receive intermediate-dose enoxaparin (1 mg/kg Subcutaneously daily or 0.5 mg/kg Subcutaneously twice daily if BMI ≥ 40).

5.3 Dose Modifications

- 1) Enoxaparin will be held if platelets decrease to $<25,000/\text{mm}^3$. Enoxaparin will resume once platelets increase to $\geq 25,000/\text{mm}^3$.
- 2) Enoxaparin will be held if fibrinogen is $<50 \text{ mg/dL}$. Enoxaparin will resume once fibrinogen increases to $\geq 50 \text{ mg/dL}$.
- 3) Enoxaparin will be held if glomerular filtration rate (GFR) $< 30 \text{ ml/min}$ calculated by the modified Cockcroft and Gault formula and resumed once the GFR is $\geq 30 \text{ ml/min}$.

All participating patients will continue the assigned doses of enoxaparin until hospital discharge or until a clinical event occurs requiring either discontinuation of anticoagulation therapy or full therapeutic dose anticoagulation therapy.

6. Randomization

Randomization to treatment arm will be allocated through a centralized randomization system in a 1:1 ratio for the standard of care versus intervention arms (low-dose versus intermediate-dose enoxaparin, respectively). The randomization process will be initiated by the study personnel who will access the web-based system and enter the patient's unique identifier, confirmation of eligibility and informed consent.

7. Assessment of Scientific Objectives

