7.1.3 Arterial thrombotic events

- 1) Acute limb arterial thrombosis, including arterial limb gangrene
- 2) Ischemic stroke (defined as any residual neurologic deficits at 24 hours)
- 3) Transient ischemic attack (defined as no residual deficits at 24 hours)
- 4) Acute (unstable) coronary syndrome
- 5) Myocardial infarction
- 6) Aortic thrombosis
- 7) Spinal cord infarction
- 8) Mesenteric artery thrombosis
- 9) Renal artery thrombosis
- 10) Hemodialysis graft (or fistula) occlusion

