7.1.4 Bleeding events

1) Major Bleeding

- a. Bleeding resulting in a decrease in hemoglobin of 2 g/dL or more over a 24-hour period
- b. Bleeding leading to a transfusion of 2 or more units of packed red blood cells
- c. Bleeding that occurs in a critical site (intracranial, intraspinal, intraocular, pericardial, intra-articular other than the operative site, intramuscular with compartment syndrome or retroperitoneal)

- d. Bleeding that leads to death
- 2) Minor Bleeding
 - a. Bleeding event that does not meet any of the criteria required for the event to be classified as a major event
- 7.1.5 Admission to the intensive-care unit
- 7.1.6 Acute renal failure
- 7.1.7 Transfusion of blood products
 - 1) Transfusion of blood products including packed red blood cells, platelets, cryoprecipitate and fresh frozen plasma will be documented and recorded
- 7.1.8 Laboratory Assessments
 - 1) Daily labs will be obtained including complete blood count with differential, prothrombin time, partial thromboplastin time, D-dimer, fibrinogen, lactate dehydrogenase, C-reactive protein, ferritin, aspartate aminotransferase, alanine aminotransferase, alkaline phosphatase, and serum creatinine
 - 2) Thromboelastography (TEG) will be obtained within 24 hours of enrollment and weekly thereafter
 - 3) Blood samples for exploratory laboratory tests will be obtained within 24 hours of enrollment and weekly thereafter. Exploratory tests will include thrombin generation, cell free DNA, and PAI-1.

8. Withdrawal or Termination

Any participant who wishes to withdraw from the study may do so at any time. If a participant chooses to withdraw from the study, no new data about that participant will be collected for study purposes. A participant may also withdraw authorization for the researchers to use his or her data that has already been collected (other than data needed to keep track of the withdrawal, including demographic data), but the participant must do this in writing to the site principal investigator.

The study may be terminated at any time by the Principal Investigator if it is deemed continuation of the protocol will not yield statistically or scientifically useful data.

9. Study Management

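### The restart rule in section 5.3 item 3 relies on calculated GFR alone and makes no provision for creatinine lowered by dialysis

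*Combined protocol and SAP*

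**What the plan says.** Section 5.3 item 3 sets both the hold and the restart by one number. Enoxaparin stops below a GFR of 30 ml/min, "calculated by the modified Cockcroft and Gault formula and resumed once the GFR is" 30 ml/min or more. The item does not mention renal replacement therapy, stability of creatinine, or recovery of the patient's own kidneys. The modified formula is not printed.

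Other places bear on the point:

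- The closing paragraph of 5.3 continues the assigned dose to discharge or "until a clinical event occurs requiring either discontinuation of anticoagulation therapy" or a change to full therapeutic dosing. Dialysis is not named.
- Section 4.2 excludes patients with a GFR below 30 ml/min and those the investigator considers at increased bleeding risk, but it acts at entry only: "Subjects meeting any of the exclusion criteria at baseline screening will be excluded".
- The tracked outcomes include "7.1.6 Acute renal failure", so renal failure during the study is foreseen.
- Section 7.1.8 has daily laboratory tests that include "aspartate aminotransferase, alanine aminotransferase, alkaline phosphatase, and serum creatinine", so the calculated GFR can be refreshed every day.
- The only mention of dialysis is an arterial outcome in 7.1.3, "Hemodialysis graft (or fistula) occlusion".

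**The concern.** The protocol treats a GFR below 30 ml/min as unsuitable both for entry and for continued dosing. Cockcroft-Gault infers GFR from creatinine, and the inference fails when a machine is clearing the creatinine. A patient who develops renal failure after entry and is then dialysed can show a calculated value above 30 with no return of native function. At that moment the rule does not merely stay silent: it states that enoxaparin is resumed.

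What is at stake is the safety of critically ill patients, in a trial that chose an intermediate dose because of bleeding risk (3.2) and lists major bleeding among its secondary objectives (2.2). The dose restarted is generally larger in the intervention arm. No anti-Xa level is among the tests in 7.1.8, so no listed test measures enoxaparin exposure directly.

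**Working it through.** **1. The plan's own figure.** Section 10 gives 82 per arm for 40% against 20% with 80% power. Two-sided alpha of 0.05 is assumed, because none is stated. With pooled variance and no continuity correction:

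n = [1.96 × √(2 × 0.3 × 0.7) + 0.8416 × √(0.4 × 0.6 + 0.2 × 0.8)]² / 0.2² = (1.270 + 0.532)² / 0.04 = 81.2, rounded up to 82.

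The figure reproduces, and nothing in it depends on the renal rule.

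**2. Creatinine at which the rule says restart.** The standard formula is used because the modified one is not printed: GFR = (140 − age) × weight / (72 × creatinine), times 0.85 for women. Setting GFR to 30 for three assumed patients:

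| Assumed patient | Calculation | Creatinine at 30 ml/min |
|---|---|---|
| Man, 65 y, 80 kg | 75 × 80 / (72 × 30) | 2.78 mg/dL |
| Woman, 70 y, 70 kg | 0.85 × 70 × 70 / (72 × 30) | 1.93 mg/dL |
| Man, 70 y, 90 kg | 70 × 90 / (72 × 30) | 2.92 mg/dL |

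For the third patient, a creatinine of 4.0 gives 6300 / 288 = 21.9 ml/min (hold). If dialysis brings it to 2.0, the result is 6300 / 144 = 43.8 ml/min (restart, at 90 mg daily in the intervention arm).

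**3. How long the rule would read restart.** If continuous dialysis keeps creatinine at or below the threshold, every daily sample reads restart.

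For intermittent dialysis without recovery, assume a post-session value of 1.5, 2.0 or 2.5 mg/dL, a rise of 0.5, 1.0 or 1.5 mg/dL per day, and samples on days 0, 1 and 2. The number of the three samples at or above 30 ml/min is:

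| Post-session value | Man 65 y, 80 kg (rise 0.5 / 1.0 / 1.5) | Woman 70 y, 70 kg (rise 0.5 / 1.0 / 1.5) |
|---|---|---|
| 1.5 | 3 / 2 / 1 | 1 / 1 / 1 |
| 2.0 | 2 / 1 / 1 | 0 / 0 / 0 |
| 2.5 | 1 / 1 / 1 | 0 / 0 / 0 |

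Day 0 is drawn just after the session. If it is dropped, each non-zero count falls by one: the man still has a restart reading in 3 of 9 combinations, the woman in none.

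**4. Dose restarted (5.2, within the 40 to 150 kg limits of 4.2).**

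- 80 kg, BMI below 40: 80 against 40 mg daily, a ratio of 2.0.
- 150 kg, BMI of 40 or more: 150 against 60 mg daily, a ratio of 2.5.
- 40 kg, BMI below 40: 40 against 40 mg daily, no difference.

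**5. Frequency.** The documents give no rate of dialysis. Assumed rates of 1%, 5% and 20% of 164 patients give 1.6, 8.2 and 32.8 patients dialysed during the study. This is a range of assumptions, not an estimate. Those wrongly restarted would be a subset.

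**The case against.** The strongest reply is that a clinician, not a formula, gives the drug. Acute renal failure is on the study's own list of events, so renal failure needing dialysis can fairly be read as a clinical event under the closing clause of 5.3. Item 3 also speaks of GFR, and reading a dialysed creatinine as GFR is the least sensible interpretation. Much of this stands: the gap does harm only if the rule is followed mechanically. But the clause depends on the event requiring discontinuation, does not name dialysis, and leaves the stated restart condition unqualified.

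Second, the key clinical step and all creatinine values come from outside the documents, and the intermittent-dialysis counts depend on when the sample is drawn. That also stands. With intermittent dialysis the rising daily creatinine can restore the hold, so sustained exposure is plausible mainly with continuous dialysis.

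Third, no harm is demonstrated. A reader might infer that enoxaparin at these doses accumulates under dialysis and causes bleeding. The documents contain nothing on this, and the working counts restart readings and milligrams, not drug levels or bleeds.

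**Conclusion.** The gap is real but minor. As written, item 3 can restart study enoxaparin, at 1 mg/kg daily in the intervention arm, in a dialysed patient whose own GFR remains below the protocol's limit. Neither the closing clause of 5.3 nor the entry-only exclusions of 4.2 correct this. The conclusion rests on the literal text and on the general knowledge that dialysis lowers creatinine without recovery. The thresholds also assume the standard formula.

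Three stronger readings are not supported:

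- **That the problem is rare, or common.** It needs entry at 30 ml/min or more, later renal failure, dialysis, a sufficient fall in creatinine and no intervention by a clinician. That chain suggests few patients, but no rate is given. The graft-occlusion item in 7.1.3 may be generic and supports no rate.
- **That the randomised comparison is biased, or that it is untouched.** The rule is the same in both arms, but the restarted dose generally is not. An effect on the bleeding comparison is possible and cannot be quantified from the documents.
- **That sample size or power is affected.** They are not.

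**What to change.** Add one line to 5.3 item 3, for both arms: *Patients receiving renal replacement therapy are treated as GFR < 30 ml/min; calculated GFR is not used to resume enoxaparin until renal replacement has stopped and the treating clinician judges that native kidney function has recovered to ≥ 30 ml/min.* Apply the same reading to the GFR exclusion in 4.2. That addition matters only for a patient whose calculated value at screening is held up by dialysis; others are already excluded.

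A purely numerical restart condition is tempting but works less well:

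- Two consecutive values at or above 30 would still restart 3 of the 18 no-recovery series above, if these are taken as the days after the last session (the man, from 1.5 rising 0.5 or 1.0, and from 2.0 rising 0.5).
- Requiring also that values are not rising blocks all 18, but delays patients who have recovered. Take the 65-year-old, 80 kg man with an assumed true GFR of 40, a starting creatinine of 1.5 and a distribution volume of 48 L. His plateau is 6000 / (72 × 40) = 2.08 mg/dL, and the daily rate constant is 40 × 1440 / 48,000 = 1.2. Creatinine on day t is 2.08 − 0.58 × exp(−1.2t), which gives 1.5, 1.9, 2.0, 2.1, 2.1 on days 0 to 4. To one decimal, the first non-rising pair is complete only on day 4, although his GFR is 40 throughout.

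The cost is one line and one clause, with no new tests, visits or patients. The downsides should be accepted openly. Dialysed patients stay off study enoxaparin longer, which carries some thrombotic risk, since the protocol itself says "Pharmacologic thromboprophylaxis is standard of care for patients admitted to the hospital with severe respiratory illness". Any other prophylaxis the clinician chooses meanwhile slightly dilutes the dose contrast. Because the trial is open-label, the judgement of recovery is made with the arm known, so its date and basis should be recorded.

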7.1 Study Outcome Measures

This study will track clinical events of interest

7.1.1 All-cause mortality at 30 days from enrollment date

- 1) In-hospital mortality will be determined by chart review
- 2) Out-of-hospital mortality will be determined by chart review or via telephone encounter by a trial investigator

7.1.2 Venous thrombotic events

- 1) Symptomatic DVT
- 2) Pelvic DVT or inferior vena cava DVT
- 3) Superior vena cava thrombosis (SVC syndrome)
- 4) Pulmonary embolism
- 5) Cerebral venous thrombosis
- 6) Retinal vein thrombosis
- 7) Mesenteric venous thrombosis
- 8) Adrenal hemorrhage/adrenal vein thrombosis
- 9) Renal vein thrombosis
- 10) Line-related venous thrombosis

7.1.3 Arterial thrombotic events

- 1) Acute limb arterial thrombosis, including arterial limb gangrene
- 2) Ischemic stroke (defined as any residual neurologic deficits at 24 hours)
- 3) Transient ischemic attack (defined as no residual deficits at 24 hours)
- 4) Acute (unstable) coronary syndrome
- 5) Myocardial infarction
- 6) Aortic thrombosis
- 7) Spinal cord infarction
- 8) Mesenteric artery thrombosis
- 9) Renal artery thrombosis
- 10) Hemodialysis graft (or fistula) occlusion

7.1.4 Bleeding events

1) Major Bleeding

- a. Bleeding resulting in a decrease in hemoglobin of 2 g/dL or more over a 24-hour period
- b. Bleeding leading to a transfusion of 2 or more units of packed red blood cells
- c. Bleeding that occurs in a critical site (intracranial, intraspinal, intraocular, pericardial, intra-articular other than the operative site, intramuscular with compartment syndrome or retroperitoneal)

- d. Bleeding that leads to death
- 2) Minor Bleeding
 - a. Bleeding event that does not meet any of the criteria required for the event to be classified as a major event
- 7.1.5 Admission to the intensive-care unit
- 7.1.6 Acute renal failure
- 7.1.7 Transfusion of blood products
 - 1) Transfusion of blood products including packed red blood cells, platelets, cryoprecipitate and fresh frozen plasma will be documented and recorded
- 7.1.8 Laboratory Assessments
 - 1) Daily labs will be obtained including complete blood count with differential, prothrombin time, partial thromboplastin time, D-dimer, fibrinogen, lactate dehydrogenase, C-reactive protein, ferritin, aspartate aminotransferase, alanine aminotransferase, alkaline phosphatase, and serum creatinine
 - 2) Thromboelastography (TEG) will be obtained within 24 hours of enrollment and weekly thereafter
 - 3) Blood samples for exploratory laboratory tests will be obtained within 24 hours of enrollment and weekly thereafter. Exploratory tests will include thrombin generation, cell free DNA, and PAI-1.

8. Withdrawal or Termination

Any participant who wishes to withdraw from the study may do so at any time. If a participant chooses to withdraw from the study, no new data about that participant will be collected for study purposes. A participant may also withdraw authorization for the researchers to use his or her data that has already been collected (other than data needed to keep track of the withdrawal, including demographic data), but the participant must do this in writing to the site principal investigator.

The study may be terminated at any time by the Principal Investigator if it is deemed continuation of the protocol will not yield statistically or scientifically useful data.

9. Study Management

It is expected that the IRB will have the proper representation and function in accordance with federally mandated regulations. The IRB should approve the consent form and protocol. In obtaining and documenting informed consent, the investigator should comply with the applicable regulatory requirement(s) and should adhere to Good Clinical Practice (GCP) and to ethical principles that have their origin in the Declaration of Helsinki. Before recruitment and enrollment onto this study, the patient will be given a full explanation of the study and will be

given the opportunity to review the consent form. Each consent form must include all the relevant elements currently required by the FDA Regulations and local or state regulations. Once this essential information has been provided to the patient and the investigator is assured that the patient understands the implications of participating in the study, the patient will be asked to give consent to participate in the study by signing an IRB-approved consent form. Prior to a patient's participation in the trial, the written informed consent form should be signed and personally dated by the patient or the patient's legally acceptable representative, and by the person who conducted the informed consent discussion.

10. Statistical analysis and considerations

The null hypothesis is that intermediate-dose LMWH (intervention arm) will have a mortality rate that is not less than low-dose LMWH (standard of care arm). A sample size of 82 patients to each arm of the study are needed to have 80% power when testing a difference of 20% (40% vs 20% for the two arms). Mean with SD and frequencies for all variables will be reported for each arm. A chi-square test will be conducted to test the mortality difference between the two arms.

Exhibit 1

Modified ISTH Overt DIC Score	
Laboratory Results	Points
Platelet Count	
> 100,000/ μ L	0
< 100,000/ μ L and \geq 50,000 / μ L	1
< 50,000 / μ L	2
D-Dimer	
No increase, \leq 0.50 mcg/mL	0
Moderate increase, >0.50 and <3.00 mcg/mL	2
Strong increase, \geq 3.00 mcg/mL	3
Prothrombin time	
Prolonged < 3 sec	0
Prolonged 3 to 5 sec	1
Prolonged \geq 6 sec	2
Fibrinogen level	
> 100 mg/dL	0
< 100 mg/dL	1
Interpretation of Score	

If \geq 3: compatible with COVID-19-associated coagulopathy
If $<$ 3: not suggestive of COVID-19-associated coagulopathy

References

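### Does a directional null, tested by a plain chi-square with no stated alpha, leave the mortality test undefined?

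*Combined protocol and SAP*

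**What the plan says.** Section 10 is the whole statistical plan, and it is a few sentences long. Its null is directional, namely that intermediate-dose LMWH "will have a mortality rate that is not less than low-dose LMWH (standard of care arm"). The analysis sentence is not: "A chi-square test will be conducted to test the mortality difference between the two arms". The sample size sentence reads "A sample size of 82 patients to each arm of the study are needed to have 80% power when testing a difference of 20" percentage points, with rates of 40% and 20% that are not assigned to named arms. Section 10 also promises descriptive statistics, including frequencies, for each arm.

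No alpha, sidedness or choice about continuity correction appears anywhere in the document.

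Elsewhere the question is put neutrally. Objective 2.1 begins "The primary objective of the study is to compare all-cause mortality of hospitalized patients with COVID-19 coagulopathy". Section 1 says the study "is designed to compare the safety and efficacy of two LMWH dosing protocols", and Section 3.2 adds: "The relative safety and efficacy of low-dose prophylactic LMWH versus higher doses of LMWH is unknown".

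**The concern.** A null of the form 'not less than' can be rejected only by lower mortality on intermediate dose. A chi-square on a 2×2 table rejects for a large difference in either direction, so a significant excess of deaths on intermediate dose would be a significant chi-square without being evidence against the null as written. With no alpha stated, the wording could also be taken to invite a one-sided 5% test.

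Two things would then be at stake in an open-label trial with a single inferential analysis:

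- **Benefit.** A result significant at one-sided 5% but not at two-sided 5% could be claimed or not, with the choice made after the data are known.
- **Harm.** An excess of deaths on intermediate dose would be visible, but its standing as a tested conclusion would be unclear. This seems awkward in a protocol that treats relative safety and efficacy as unknown.

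**Working it through.** **Inputs.** From Section 10: 82 per arm, 80% power, 40% vs 20%. From Section 6: 1:1 allocation. Alpha is not in the document, so it is treated as unknown and a range is tried. Assigning 40% to the low-dose arm is an inference from the direction of the null; the sample size formula is symmetric and does not depend on it.

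**Step 1. Reproduce the plan's figure.** The pooled formula without continuity correction, with mean rate 0.30, is

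n = [z_α √(2 × 0.30 × 0.70) + 0.8416 √(0.40 × 0.60 + 0.20 × 0.80)]² / 0.20²

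- z_α = 1.96: (1.96 × 0.6481 + 0.8416 × 0.6325)² / 0.04 = (1.2702 + 0.5323)² / 0.04 = 81.2, so **82**. This matches the plan.
- z_α = 1.645: (1.0660 + 0.5323)² / 0.04 = 63.9, so 64. This does not match.

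Other variants at 80% power:

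| Critical value | Pooled | Pooled, continuity-corrected | Unpooled | Arcsine |
|---|---|---|---|---|
| 1.96 (two-sided 5% or one-sided 2.5%) | **82** | 91 | 79 | 81 |
| 1.645 (one-sided 5%) | 64 | 74 | 62 | 64 |

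Two-sided 2.5% gives 99 and one-sided 10% gives 47 (pooled, uncorrected). Among the variants tried, only the pooled uncorrected formula at 1.96 returns 82, and no one-sided 5% variant comes near it. The sample size therefore points both to the critical value and to an uncorrected test.

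**Step 2. Power at 82 per arm.** The normal approximation at 1.96 gives (0.20 × √82 − 1.2702) / 0.6325 = 0.855, which is power of 80.4%. Exact binomial enumeration of the uncorrected test gives 80.7%. At one-sided 5% the same calculations give 88.1% and 88.6%, neither of which is the stated 80%.

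**Step 3. The two natural readings give one rule for benefit.** On one degree of freedom the chi-square is z². A two-sided p below 0.05 with fewer deaths on intermediate dose means z > 1.96, which is exactly the one-sided 2.5% rejection region for the directional null.

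Take 33 of 82 low-dose deaths (40.2%, close to the planned 40%). With 21 intermediate-dose deaths:

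- difference = 12/82 = 0.1463
- pooled rate = 54/164 = 0.3293
- standard error = √(0.3293 × 0.6707 × 2/82) = 0.0734
- z = 1.99, two-sided p = 0.046

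With 22 deaths the difference is 11/82 = 0.1341, the standard error 0.0737 and z = 1.82, short of 1.96. The cut-off is 21 under either reading. With a common rate of 40%, the exact type I error of the two-sided test is 4.75%, about 2.4% in each direction.

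**Step 4. Harm direction.** With 46 vs 33 deaths the difference is 13/82 = 0.1585, the pooled rate 79/164 = 0.4817, the standard error 0.0780 and |z| = 2.03. The two-sided p is 0.042; the one-sided p for the stated null is 0.979. The plan commits to reporting frequencies by arm and to testing the difference, so both the excess and its chi-square p-value would appear in the report.

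**Step 5. Continuity correction.** If it were applied, 21 deaths against 33 would give p = 0.068, the cut-off would become 20, and exact power at 82 would be 75.9%. This is the one unstated choice that could move a borderline result. The stated 82, rather than 91, indicates that the uncorrected test was meant.

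**The case for a change.** The strongest case for a change is that the sentences in Section 10 are the decision rule, and that a reader should not have to work back from the sample size to find alpha. The null as worded gives someone a footing to argue for one-sided 5%. Against 33 of 82 deaths that reading would accept 23 deaths (z = 1.647, one-sided p = 0.0498, two-sided p = 0.0996). At the planned 40% vs 20%, the chance of a result that is significant only on that reading is 7.9%; at assumed rates of 40% vs 25% and 40% vs 30% it is 12.9% and 11.8%. If the arms do not differ (common rates of 20% to 40%), the false-benefit rate would rise from 2.4–2.5% to 4.8–5.2%.

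The arithmetic is right, but it describes a hypothetical misuse. Nothing in the document proposes a one-sided 5% test, and the stated sample size contradicts one.

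The supposed clash with Objective 2.1 does not hold either. 'Compare' is ordinary wording for an objective and does not exclude a directional hypothesis. Calling the relative effects unknown expresses equipoise, not the sidedness of a test.

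Two things stand. Alpha and sidedness are indeed not written down. And a significant excess of deaths on intermediate dose would not, in strict terms, reject the null as worded. The second is a matter of what the finding is called, since the frequencies and the p-value would be reported in any case.

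**Conclusion.** No change to the plan is needed. Section 10 leaves a gap in its wording that an analyst fills in the conventional way: an uncorrected chi-square at two-sided 5%, with direction read from the reported rates, which for benefit is the directional null tested at one-sided 2.5%. On that basis 82 per arm is correct, exact power is 80.7%, and the benefit cut-off against 33 of 82 deaths is 21. Writing alpha into the plan would alter none of these.

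This rests on three inferences: alpha is taken from the sample size because the document does not state it; the test is taken as uncorrected because 82 fits that formula and 91 would be needed otherwise; and the 40% rate is taken to belong to the low-dose arm. What remains open is whether a significant excess of deaths on intermediate dose would be called a formal conclusion of harm. That affects how such a result is described, not whether it is seen or how it is calculated.
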